### **ANNEX 3.5: Bosutinib SmPC**

Available online:

<http://wvpartner.pfizer.com/webviewer/labelcentral/Labels/EUBPI/France/French/FRA%20BOSU%2031%20MLG%20LONGUES%20%20v005%2015Nov2018.pdf>

### **ANNEX 3.7: Registry of non-inclusion**

## **Registry of non-inclusion**

### **OBJECTIVES OF THE REGISTRY OF NON-INCLUSION**

The registry of non-inclusion makes it possible to compare patients who will be included in the BosEVAL study to patients who will not be included.

This comparison makes it possible to have an evaluation of an inclusion bias, as well as to measure their impact on the representativeness of the studied population.

Consequently, the statistical results will be totally utilizable and can be published.

### **INSTRUCTIONS FOR COMPLETING THE REGISTRY OF NON-INCLUSION**

the registry of non-inclusion is to be completed during the inclusion period of the BosEVAL study for all adult patients who satisfy criteria for inclusion and for non-inclusion but who have not wanted to participate in the study.

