
NATURE AND DURATION OF STUDY
	
This is a national, observational, descriptive, prospective, multi-centre study conducted in Metropolitan France in adult patients treated for chronic phase, accelerated or blast phase Philadelphia chromosome positive (Ph+/-) CML, previously treated with one or more TKIs and for whom imatinib, dasatinib or nilotinib are not considered as appropriate treatments. The study will be conducted in all centres involved in management of CML, i.e. about twenty (20) centres are expected.
 
The study will be offered to all patients who satisfy criteria for eligibility up to the end of the recruitment period. Eligible patients but not included in the study will be recorded in a non-inclusion registry.
 
Patients will be followed prospectively throughout the duration of the study (3-year follow-up) starting from their inclusion in the study. Follow-up data will be collected at follow-up visits conducted in the setting of usual management, estimated at every 3 months independently of discontinuations, changes or discontinuations of treatment possibly implemented. Therapeutic management of the patient will not be

	
changed by participation in the study.

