#### **9.4.1.7. Registry of non-inclusion:**

Patients eligible but not included must be recorded in a non-inclusion registry (*see ANNEX 3.7: Registry of non-inclusion*), with a minimum of parameters collected:

- Demographic characteristics (year of birth, gender),
- Reason for non-inclusion.

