## **9.5. Study sample size**

Since the descriptive objective of this study does not involve the hypothesis of specific research, it is not necessary to calculate a minimum sample size population of participating

patients. Furthermore, since CML is a rare disease, a minimum number of patients is not expected.

Based on the number of monthly prescriptions of Bosulif® (sponsor data) and taking into account the future start-up of a competitive study, a total of one hundred (100) patients included in the study appears to be a reasonable objective. Participating doctors should include on average 5 patients in the study, with no distinction between phases of CML at inclusion.

However, it is shown that about one hundred patients would make it possible to have acceptable precision, precision corresponding to half of a 95% confidence interval (CI):

- $\leq 10\%$  to estimate a percent of patients presenting with a given event (Wald asymptotic method without a continuity correction – hypothesis of a 50% rate)
- Of 10% in order to estimate median survival (Greenwood formula under the hypothesis of absence of data censored at the right before median survival and occurrence of a single event at a time).

Consecutive inclusion of patients who satisfy eligibility criteria up to the end of the inclusion period estimated at 2 years will ensure the representativeness of patients in the study.

In order to ensure compliance with this consecutiveness, a registry of non-inclusion will be set up. Patients eligible but not included in the study must be recorded in this registry and throughout the period of inclusion. A minimum of parameters will be collected.

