#### **9.6.1.1. Channel of CRF and data entry**

Data collected by the participating doctor at time of inclusion and in the follow-up of patient visits will be recorded directly in the eCRF of the study.

For each centre, a registry will be made available to investigators to list patients eligible but not included: reason for non-inclusion, age, gender, and disease. Only one order number will be used to designate such patients in a manner so that they may be identified. Patients not included will be compared to patients included in the database of characteristics recorded in order to verify the absence of a selection bias or of inclusion bias.

Adverse events will be collected *via* the eCRF by doctors at the usual follow-up consultations, for all patients in the study. When applicable, requests for further information from the Pfizer pharmacovigilance department will be sent to the person who reported the event (participating doctor). All reports (initial and follow-up reports) will be grouped together via a centre number and patient number.

Patients' questionnaires on measurement of compliance and patients' questionnaires on measurement of quality of life will be sent to the CRO in charge of their data entry.

After validation of the database by Pfizer, paper questionnaires will undergo double data entry with the CRO's own software for patients' questionnaires in paper format. Periodic update reports on progression of data entry will be edited by the CRO and sent to Pfizer.

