### **9.9.2. Selection bias of patients**

The representativeness of the sample of the study compared to the target population is basic in order to be able to extrapolate results of the study to the target population. The representativeness of the sample depends on internal validity (precision of estimates and selection criteria of study population – the patients) and the outside validity (plan and fluctuations of sampling).

The representativeness of patients included is a potential selection bias in observational studies. Conscious selection or not of patients in the study by participating doctors is inevitable. Participating doctors will be asked to include sequentially and exhaustively all patients who satisfy eligibility criteria for the study up until the end of the inclusion period in order to limit this bias. Parameters on representativeness of patients included will be controlled by the set-up of a registry of non-inclusion up until the end of the inclusion period.

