**CHARACTERISTICS OF PATIENTS NOT INCLUDED IN THE STUDY**

CENTRE No.: |\_|\_|

	Date of consultation	Date of birth	Gender	Reason for non-inclusion
1	_ _  /  _ _  /  _ _ _ _  (DD/MM/YYYY)	_ _  /  _ _ _ _  (MM/YYYY)	 Male  Female	 Patient refusal  Other, specify: ____
2	_ _  /  _ _  /  _ _ _ _  (DD/MM/YYYY)	_ _  /  _ _ _ _  (MM/YYYY)	 Male  Female	 Patient refusal  Other, specify: ____
3	_ _  /  _ _  /  _ _ _ _  (DD/MM/YYYY)	_ _  /  _ _ _ _  (MM/YYYY)	 Male  Female	 Patient refusal  Other, specify: ____
4	_ _  /  _ _  /  _ _ _ _  (DD/MM/YYYY)	_ _  /  _ _ _ _  (MM/YYYY)	 Male  Female	 Patient refusal  Other, specify: ____
5	_ _  /  _ _  /  _ _ _ _  (DD/MM/YYYY)	_ _  /  _ _ _ _  (MM/YYYY)	 Male  Female	 Patient refusal  Other, specify: ____

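### The Annex 3.7 instruction limits the non-inclusion registry to patients who declined, contradicting the protocol body and the registry form; the registry field lists also disagree on a disease item

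*Protocol*

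**What the plan says.** The body of the protocol is consistent about who goes into the registry. The Synopsis states "Eligible patients but not included in the study will be recorded in a non-inclusion registry", and section 9.2 says the same in almost the same terms. Section 9.4.1.7 makes it an obligation: "Patients eligible but not included must be recorded in a non-inclusion registry". Section 9.5 adds the time frame: "Patients eligible but not included in the study must be recorded in this registry and throughout the period of inclusion". Section 9.6.1.1 also describes the registry as listing patients who were eligible but not included. None of these restricts the reason.

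The instruction printed with the form in Annex 3.7 says the registry is to be completed "for all adult patients who satisfy criteria for inclusion and for non-inclusion but who have not wanted to participate in the study". The form that follows gives two reasons to tick: patient refusal, or "Other, specify".

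On content, section 9.6.1.1 lists "reason for non-inclusion, age, gender, and disease". Section 9.4.1.7 sets a smaller minimum: "Demographic characteristics (year of birth, gender") and the reason for non-inclusion. The form has columns for date of consultation, month and year of birth, gender and reason.

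On purpose, section 9.5 uses the registry to check that inclusion is consecutive, and section 9.6.1.1 uses it to compare included with non-included patients for selection bias. Section 9.9.2 makes it the control for a bias it describes plainly: "Conscious selection or not of patients in the study by participating doctors is inevitable".

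**The concern.** The threat named in section 9.9.2 is the doctor's choice of whom to include. A patient who was never asked has not declined, so under the Annex 3.7 instruction that patient does not belong in the log. A log of refusals measures patients' choices and is silent on doctors' choices.

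The annex matters more than its position suggests, because it is the text attached to the form that sites fill in. If sites follow it, the comparison in section 9.6.1.1 would set included patients against refusers, and the check of consecutive inclusion would count only patients who were offered the study. A reassuring result could then be reported although the group of interest was never recorded.

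The missing disease item narrows the comparison further. Section 9.5 includes patients without distinction of CML phase, while section 9.7.1 analyses the data by phase and treatment line. With only age and gender in common, the registry gives no view of whether the included patients differ from the others in their disease.

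**Working it through.** The protocol states no figure on this point, so the check is a comparison of text.

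1. Who is to be logged.
   - Synopsis, sections 9.2, 9.4.1.7, 9.5 and 9.6.1.1: eligible patients not included, reason unrestricted (five places).
   - Annex 3.7, statement of objectives: included patients are compared with those not included, again without limiting the reason.
   - Annex 3.7, completion instruction: eligible patients who did not want to take part (one place).
   - Annex 3.7, form: refusal or another specified reason, so the form can hold cases that the instruction leaves out.

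2. What follows for each type of eligible, non-included patient.
   - Asked and declined: logged under both the body text and the instruction.
   - Not approached, or missed: logged under the body text, not under the instruction.
   - Doctor decided against inclusion: logged under the body text, not under the instruction.

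   The last two groups are the ones through which doctor-driven selection acts.

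3. Which fields are recorded, taking the four items of section 9.6.1.1 in turn.
   - Reason: in section 9.4.1.7 and on the form.
   - Age: in section 9.4.1.7 as year of birth, on the form as month and year of birth.
   - Gender: in both.
   - Disease: in neither.

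   The form therefore carries 3 of the 4 items. Reason exists only for patients who were not included, so it cannot be compared between groups. The consultation date is not a patient characteristic. That leaves age and gender.

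4. Whether another step would catch under-logging. Section 9.8.2 has monitors check that doctors understand and comply with the protocol, but the specific checks it lists do not include the registry.

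The one nearby figure is the precision statement in section 9.5. At n = 100 and a 50% rate the 95% half-width is 1.96 × √(0.5 × 0.5 / 100) = 0.098, which agrees with the stated bound of 10%. It describes sampling error only and has no bearing on selection.

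**The case against.** The strongest reply is that one loosely worded sentence stands against the rest of the protocol. The body text is uniform, section 9.9.2 asks doctors to include all eligible patients in sequence, the annex's own objectives speak of patients not included, and a refusal-only log would not need a second reason box. The English is also visibly a rough translation, so a reading that hangs on one verb is fragile. Most of this stands. A reader might infer that the registry cannot detect doctor-driven selection at all. The documents do not support that, because a centre working from the body text could log such patients under the other-reason option. What remains is that the completion instruction, taken as written, says something different, and nothing tells a site which text prevails.

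Two further inferences should be resisted. First, section 9.6.1.1 says only disease; it does not promise CML phase. Since every eligible patient has CML, a bare disease entry might separate no one, and deleting the word there would also remove the inconsistency. Second, a reader might count patients who stopped bosutinib or died before consent among those wrongly left out. Signed consent is itself an inclusion criterion (section 9.2.1) and the form is built around a consultation date, so it is unclear whether the protocol regards such patients as eligible.

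**Conclusion.** The point holds as an internal contradiction with a practical consequence. The Annex 3.7 instruction is narrower than the protocol body and than its own form. Followed literally, it leaves unrecorded the patients through whom the selection described in section 9.9.2 would act. Separately, sections 9.4.1.7 and 9.6.1.1 and the form disagree on the disease item, and with the current form the comparison is limited to age and gender.

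The conclusion assumes that sites work from the instruction printed with the form, and that eligible means meeting the criteria other than signed consent, since otherwise no refuser could be eligible either.

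A reader might go further and conclude that the two primary percentages are biased by some amount. The documents do not support that. They give no count of patients not approached and no event rate for them, and they do not show that CML phase drives related adverse events or discontinuation. The registry collects no outcomes, so even a complete one could not measure or correct such a bias. It could only show who was left out and why.

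**What to change.** Reword the completion instruction in Annex 3.7 so that it covers all eligible patients not included in the study, whatever the reason (for example refusal, not offered, missed). Replace the two reason boxes with boxes that match, keeping a free-text option.

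Reconcile section 9.4.1.7, section 9.6.1.1 and the form on the disease item. The preferable route is to add one simple item, such as CML phase, to the form and to section 9.4.1.7. Phase is a suggestion made here, not something section 9.6.1.1 already promises, and it needs a data-protection check. If that is not wanted, remove disease from section 9.6.1.1 and acknowledge that the comparison covers age and gender only.

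The cost is one sentence, a few tick boxes on an existing form and slightly more logging by sites. The rewording needs no new data item and does not depend on the disease decision.

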**CHARACTERISTICS OF PATIENTS NOT INCLUDED IN THE STUDY**

CENTRE No.: |\_|\_|

	Date of consultation	Date of birth	Gender	Reason for non-inclusion
1	_ _  /  _ _  /  _ _ _ _  (DD/MM/YYYY)	_ _  /  _ _ _ _  (MM/YYYY)	 Male  Female	 Patient refusal  Other, specify: ____
2	_ _  /  _ _  /  _ _ _ _  (DD/MM/YYYY)	_ _  /  _ _ _ _  (MM/YYYY)	 Male  Female	 Patient refusal  Other, specify: ____
3	_ _  /  _ _  /  _ _ _ _  (DD/MM/YYYY)	_ _  /  _ _ _ _  (MM/YYYY)	 Male  Female	 Patient refusal  Other, specify: ____
4	_ _  /  _ _  /  _ _ _ _  (DD/MM/YYYY)	_ _  /  _ _ _ _  (MM/YYYY)	 Male  Female	 Patient refusal  Other, specify: ____
5	_ _  /  _ _  /  _ _ _ _  (DD/MM/YYYY)	_ _  /  _ _ _ _  (MM/YYYY)	 Male  Female	 Patient refusal  Other, specify: ____

